### 9.3 EFFICACY CRITERIA FOR TUMOR RESPONSE

N/A.

## 10. SAFETY

### 10.1 SPECIFICATION OF SAFETY PARAMETERS

The investigational device being assessed in this Study (Sklip System) is not of substantial importance in diagnosing, curing, mitigating, or treating disease. Instead, it provides a triage assessment according to a clinically accepted protocol, which is intended for confirmation by a healthcare professional. Therefore Participants enrolled in the Study are not exposed or introduced to any additional medical safety risks that would warrant scheduled screening assessments. The Participants have the option to be evaluated by a dermatology Provider via standard clinical care pathways, not part of the Study, and would be considered an unscheduled visit (Section 8.9 Unscheduled Visits).

There is minimal risk of psychological or behavioral effects that may be experienced by the Participant during the Study. At the start of enrollment for each Participant, he/she/they will have onboarding training by a Study Coordinator on how to contact a research team member to report any adverse psychological or behavioral effects throughout the duration of their enrollment.

If a Participant reports any adverse events, the investigator will immediately be informed of the event. The investigator will be responsible for assessing the reported adverse events and will be followed by a member of the Study team until resolution/stabilization. The Participant will be offered the voluntary option to withdraw from the Study and discontinue any intervention. The report will be documented in the Participant's record.

### 10.2 DEFINITIONS

#### 10.2.1 ADVERSE EVENT (AE)

An adverse event is defined as any undesirable physical, psychological or behavioral effect experienced by a Participant during their participation in an investigational Study, in conjunction with the use of the investigational

product (Sklip System). In general, this includes signs or symptoms experienced by the Participant from the time of signing the informed consent to completion of the Study. Although we do not anticipate that the intervention in this Study poses significant risk to Participants, the following AEs for this Study may include but are not limited to:

- Subjective reports of increased psychological stress induced by self-skin-examinations (SSEs)
- Subjective reports of significant changes in behavior experienced by the Participant
- Allergic reaction to the Sklip provided dermatoscopy oil (not reported to date)

#### 10.2.2 SERIOUS ADVERSE EVENT (SAE)

In alignment with the FDA guidance and 21 CFR 812.3(m), Sklip has determined that a clinical Study utilizing the Sklip System constitutes a **Non-Significant Risk Device Study**. Please refer to Section 1.3 RISK/BENEFIT ASSESSMENT.

#### 10.2.3 UNANTICIPATED PROBLEMS (UP)

The Office for Human Research Protections (OHRP) considers UPs involving risks to Participants or others to include, in general, any incident, experience, or outcome that meets all of the following criteria:

1. Unexpected in terms of nature, severity, or frequency given (a) the research procedures that are described in the protocol-related documents, such as the IRB-approved research protocol and informed consent document; and (b) the characteristics of the Participant population being studied;
2. Related or possibly related to participation in the research (“possibly related” means there is a reasonable possibility that the incident, experience, or outcome may have been caused by the procedures involved in the research); and
3. Suggests that the research places Participants or others at a greater risk of harm (including physical, psychological, economic, or social harm) than previously known or recognized.

Our Study additionally includes an unanticipated adverse device effect, any serious adverse effect on health or safety or any life-threatening problem or death caused by, or associated with, a device, if that effect, problem, or death was not previously identified in nature, severity, or degree of incidence in the investigational plan or application, or any other unanticipated serious problem associated with a device that relates to the rights, safety, or welfare of Participants (21 CFR 812.3(s))

#### 10.2.4 SEVERITY OF EVENT

The Investigator will grade the severity of each AE using, when applicable, the current version of the [CTCAE v5.0](#). In the event of an AE for which no grading scale exists, the Investigator will classify the AE as defined below:

---

**Grade 1:** Mild; asymptomatic or mild symptoms; clinical or diagnostic observations only; intervention not indicated.

**Grade 2:** Moderate; minimal, local or noninvasive intervention indicated; limiting age-appropriate instrumental ADL

**Grade 3:** Severe or medically significant but not immediately life-threatening; hospitalization or prolongation of hospitalization indicated; disabling; limiting self-care ADL.

**Grade 4:** Life-threatening consequences; urgent intervention indicated.

**Grade 5:** Death related to AE.

---

#### 10.2.5 ASSESSMENT OF CAUSALITY RELATIONSHIP TO STUDY INTERVENTION

For all collected AEs, the clinician who examines and evaluates the Participant will determine the AE's causality based on temporal relationship and his/her clinical judgment. The degree of certainty about causality will be graded using the categories below.

**Related** – The AE is known to occur with the Study intervention, there is a reasonable possibility that the Study intervention caused the AE, or there is a temporal relationship between the Study intervention and event. Reasonable possibility means that there is evidence to suggest a causal relationship between the Study intervention and the AE.

**Not Related** – There is not a reasonable possibility that the administration of the Study intervention caused the event, there is no temporal relationship between the Study intervention and event onset, or an alternate etiology has been established.

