### 10.6.3 FDA REPORTING

Some events must be reported to the FDA through the MedWatch Voluntary reporting program, even if the trial involves a commercially available agent. Events to be reported include any UPs and any SAEs with a suspected association to the Study intervention. An eligible person at the OHSU Coordinating Center will evaluate any reported UADE at the coordinating Study Site or satellite Study Site(s). The sponsor will provide to the FDA, all reviewing IRB's, and all sub-investigators an IDE Safety Report for any UADE that meets all of the following criteria: 1) an adverse effect caused by or associated with the device, 2) serious, and 3) Unanticipated. The sponsor will provide this no later than 10 working days after first notice of the effect. Thereafter, the sponsor will report any additional information concerning the effect per FDA request, and as warranted.

If the sponsor determines that the UADE presents an unreasonable risk to subjects, the sponsor will terminate all

investigations or parts of investigations that present risk as soon as possible (no later than 5 working days after the sponsor makes this determination), and no later than 15 working days after the sponsor first receives notice of the effect.

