#### 11.4.4 SAFETY ANALYSIS

Adverse events will be tabulated by the Medical Dictionary for Regulatory Activities. The severity of the AE will be assessed by National Cancer Institute (NCI) Common Terminology Criteria for Adverse Events (CTCAE) Version 5.0 criteria. Descriptive statistics using the safety evaluable population, will be used to report on all on-Study AEs, grade 3-4 AEs, treatment-related AEs, grade 3-4 treatment-related AEs, SAEs, treatment-related SAEs, and AEs

leading to discontinuation per CTCAE v5.0. Grade 3-4 laboratory abnormalities will be summarized using worst grade NCI CTCAE v 5.0 criteria.

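### The two causality categories in 10.2.5 overlap, with no rule for which prevails, so the treatment-related counts in 11.4.4 are not fixed by the protocol

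*Combined protocol and SAP*

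**What the plan says.** Section 10.2.5 asks the clinician who examines the participant to assign each AE to one of two categories, using timing and clinical judgment.

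- *Related* has three limbs. The first is that the event is a known effect of the intervention. The other two are "there is a reasonable possibility that the Study intervention caused the AE, or there is a temporal relationship between the Study intervention and event". The section then explains a reasonable possibility as evidence pointing to causation.
- *Not Related* also has three limbs. The first is "There is not a reasonable possibility that the administration of the Study intervention caused the event". The other two are "there is no temporal relationship between the Study intervention and event onset, or an alternate etiology has been established".

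There is no intermediate category, and neither this section nor any other says which category prevails when both are met.

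The classification is used in 11.4.4, which plans descriptive counts that include "treatment-related AEs, grade 3-4 treatment-related AEs, SAEs, treatment-related SAEs". Section 10.2.5 is the only AE causality scale in the protocol. Section 10.5 has relationship to the product recorded for AEs and requires every on-study AE to be documented whatever that relationship is.

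**The concern.** A two-category scale should place each event in exactly one category. Here one limb of *Related* is timing, and one limb of *Not Related* is another cause. These are different kinds of fact, and both can be true of the same event. An example from the protocol's own list is increased psychological stress, the event of special interest in 10.4.3. If it is reported after device use but is traced to something else, the assessor can cite the text for either category.

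What is at stake is the set of treatment-related rows in 11.4.4. There are four sites, and 8.1.2 allows the evaluating dermatology provider to be someone outside the study, so a shared understanding of the rule cannot be presumed. Two assessors could place the same event in opposite categories and both comply with the protocol.

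**Working it through.** The plan gives no figure on this point, so the check is one of logic.

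**Inputs, all from 10.2.5.** Four yes/no facts: K, the event is known to occur with the intervention; R, there is a reasonable possibility of causation; T, there is a temporal relationship; A, an alternate etiology is established.

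**Definitions as written.**

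- *Related* = K or R or T
- *Not Related* = (not R) or (not T) or A

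The opposite of an *or* list is an *and* list: the true complement of *Related* is (not K) and (not R) and (not T). *Not Related* negates R and T but joins the negations with *or*, and then adds A as a further sufficient limb. That is where the overlap comes from.

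**Enumeration.** Four yes/no facts give 2 × 2 × 2 × 2 = 16 patterns.

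- *Not Related* fails only when R and T are true and A is false. K is free, so 2 patterns are *Related* only.
- *Related* fails only when K, R and T are all false. A is free, so 2 patterns are *Not Related* only.
- The remaining 16 − 2 − 2 = 12 patterns meet both. None meets neither.

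Some of the 16 are implausible in practice, so the count was repeated under restrictions that favour the plan, added one after another:

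| Reading | Patterns | Both | *Related* only | *Not Related* only |
|---|---|---|---|---|
| No restriction | 16 | 12 | 2 | 2 |
| K implies R | 12 | 8 | 2 | 2 |
| and R implies T | 8 | 4 | 2 | 2 |
| and A rules out R | 6 | 2 | 2 | 2 |

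The two that remain in the last row are T true with R false, with and without an alternate etiology. The case at issue (temporal relationship, other cause established) therefore meets both definitions on every reading.

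Among the 8 unrestricted patterns in which T is true, 6 meet both, 2 are *Related* only and none is *Not Related* only. Once a temporal relationship is accepted, no event is unambiguously *Not Related*.

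**Effect on the counts.** Let a be the number of events that meet *Related* only and b the number that meet both. With every assessor following the protocol, the treatment-related count can be anything from a to a + b. The documents project neither a nor b.

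**The case against.** The strongest reply is that the scale is not mechanical. The clinician is told to use judgment as well as timing, and a clinician who sees a plain other cause has direct textual support for *Not Related* in "or an alternate etiology has been established". Part of this stands. Clear-cut events are fixed: a reasonable possibility with a temporal relationship and no other cause is *Related*, and an event with none of K, R or T is *Not Related*. It would go too far to call the whole count arbitrary. But judgment still has to be expressed in the two categories, and for an overlap event they support either answer.

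The second reply is that the protocol does not define a temporal relationship, and it need not mean any time after device use. That also stands. A reader might infer that nearly every event becomes *Related* because the examination and any biopsy follow the at-home phase, but this needs the widest meaning of the term. It also overlooks the coordinator's use of the dermatoscope in the office (3.1). A narrower meaning makes the overlap rarer but does not remove it.

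Three stronger inferences are not supported:

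- **That FDA reporting turns on this scale.** Section 10.6.3 says "Events to be reported include any UPs and any SAEs with a suspected association to the Study intervention", but it sets its own standard of suspicion and does not cite 10.2.5. UADEs have separate criteria there and are evaluated at the coordinating center. Unanticipated problems are defined in 10.2.3.
- **That the safety result as a whole cannot be interpreted.** Section 11.4.4 also tabulates all on-study AEs, grade 3-4 AEs, all SAEs and AEs leading to discontinuation, none of which uses relatedness.
- **That biopsy complications give the size of the problem.** Table 6 expects 203 malignant lesions, but the documents give no complication rate. Section 10.2.1 ties an AE to use of the device, and 8.1.2 treats biopsy as standard care outside the study, so it is open whether such complications would be recorded as AEs at all.

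**Conclusion.** The point holds in a limited form. Section 10.2.5 contradicts itself for any event that has a temporal relationship to device use and either another established cause or no reasonable possibility of device causation. For those events the class depends on the assessor. The treatment-related AE, grade 3-4 treatment-related AE and treatment-related SAE counts in 11.4.4 are therefore not determined by the protocol.

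Total AE and SAE counts, the UP and UADE criteria and the primary sensitivity and specificity analyses are not affected.

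The conclusion rests on two readings: that *or* in 10.2.5 makes each limb sufficient, and that the treatment-related rows in 11.4.4 are filled from 10.2.5, the only AE causality scale given. The pattern counts show that the overlap survives every favourable restriction tried; they are not event frequencies. How many events will fall in the overlap cannot be worked out from the documents.

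**What to change.** Reword 10.2.5 so that exactly one category applies:

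- *Related*: there is a reasonable possibility, meaning evidence that suggests causation, that the Sklip System caused the event. Timing counts as supporting evidence and is not sufficient alone.
- *Not Related*: all other events, including those whose established alternate etiology leaves no reasonable possibility of device causation.

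Align the CRF wording, and state in 11.4.4 that treatment-related means *Related* under 10.2.5. A separate field for relationship to biopsy or examination is optional; the defect is cured without it.

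The cost is protocol and CRF wording. No sample size, endpoint or accuracy analysis changes. The downside is that the related-AE count may change in either direction compared with what assessors would have recorded under the present text, so any event already classified should be reviewed under the new definitions.

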### 10.3 EXPECTEDNESS

The Investigator will be responsible for determining whether an AE is expected or unexpected. An AE will be considered unexpected if the nature, severity, or frequency of the event is not consistent with the risk information previously described for the Study agent.

### 10.4 ADVERSE EVENT LIST(S)

#### 10.4.1 ADVERSE EVENT LIST FOR SKLIP DEVICE AND SKLIP SYSTEM

Detailed information about the risks and expected AEs of the Sklip System may be found in the current edition of the manufacturer's instruction manual.

In alignment with the FDA guidance mentioned above and 21 CFR 812.3(m), Sklip has determined that a clinical Study utilizing the Sklip System constitutes a **Non-Significant Risk Device Study**. Please refer to Section 1.3 RISK/BENEFIT ASSESSMENT.

#### 10.4.2 ADVERSE EVENT LIST FOR

N/A

#### 10.4.3 KEY SAFETY CONCERNS AND/OR ADVERSE EVENTS OF SPECIAL INTEREST

All Participants			
Key safety concern/AESI:	Threshold for action:	Participant management:	Special reporting requirements:
Increased psychological stress/burden	Participant reports significant increase in psychological stress and requests for additional action	Participant will be offered the option to discontinue the Study or be offered a referral to an appropriate provider within the Study Site provider network	N/A

### 10.5 TIME PERIOD AND FREQUENCY FOR EVENT ASSESSMENT AND FOLLOW-UP

The occurrence of an UP, AE or SAE may come to the attention of Study personnel during Study visits and interviews of a Study Participant presenting for medical care, upon review by a Study monitor, or during an audit. All AEs including local and systemic reactions not meeting the criteria for SAEs will be captured on the appropriate CRF. Information to be collected includes event description, time of onset, clinician's assessment of severity, seriousness, expectedness, relationship to Study product (assessed only by those with the training and authority to make a diagnosis), and date of resolution/stabilization of the event. All AEs occurring while on Study must be documented appropriately regardless of relationship. All AEs will be followed to adequate resolution.

Any medical condition that is present at the time that the Participant is screened will be considered as baseline and not reported as an AE. However, if the Study Participant's condition deteriorates at any time during the Study, it will

be recorded as an AE after enrollment. Changes in the severity of an AE will be documented to allow an assessment of the duration of the event at each level of severity to be performed. AEs characterized as intermittent require documentation of onset and duration of each episode. The Investigator will record all reportable events with start dates occurring any time after enrollment until the last day of Study participation. AEs will be evaluated using the current version of the [CTCAE v5.0](#). If a Participant electively schedules a follow up visit with a provider, the investigator will inquire about the occurrence of AE/SAEs. Events will be followed for outcome information until resolution or stabilization.

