## SYNOPSIS

Full Study Title	At-home dermoscopy artificial intelligence for optimizing early triage of skin cancers and atypical melanocytic nevi with uncertain malignant potential
Protocol #	STUDY00023727
Study Type	Prospective single-arm open-label multicenter research Study
Study Sample Size	310 Participants
Lead Study Site	Oregon Health and Sciences University (OHSU) in Portland, Oregon [name] (Department of Dermatology) PI: [name] [name] ( [contact] )
Satellite Study Site(s) Governance	OHSU IRB will not be responsible for governing any of the Satellite Study Sites. Their governance will be a third-party IRB using this IRB Protocol for guidance.
Study Site #2	Skin Cancer Center [name] PI: [name] MD FAAD ( [contact] )
Study Site #3	The Skin Center Dermatology Group [name] PI: [name] [name] FAAD ( [contact] )
Study Site #4	The Private Practice of [name] D.O. P.A. [name] PI: [name] DO FAOCD ( [contact] )
At-Home Phase Duration	Up to 14 days, completed by Participants at their home address
In-Person Phase Duration	Up to 28 days, completed by Participants and Study Coordinators in-office
Enrollment Duration	Up to 90 days
Abbreviated Definitions in Sequential Order	Sklip System (Sklip dermatoscope device and SMSA (used in the Sklip App)) SMSA: Sklip Mole Scanning Algorithm SCI: Smartphone clinical images (non-medical-device assisted) DDI: Digital dermoscopy images PSLC(s): Pigmented skin lesion(s) of concern FDA: United States Food and Drug Administration PMLS: Participant Mole Log Sheet SaMD: Software as a Medical Device API: Application Program Interface DP: Dermatology Provider APP: Advanced Practice Practitioner (Physicians Associate or Nurse Practitioner) PCP: Primary Care Provider MD3PC: Modified dermoscopy three-point checklist DRFs: Dermoscopic remarkable features (based on the MD3PC)

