Study Coordinators at each Study Site will conduct regular EMR chart reviews to track Participant requests to begin their In-person Phase, after the Participant has completed their the At-home Phase. These chart reviews will be conducted systematically every 7 days following Participant enrollment. Participant EMRs will be monitored for up to 28 days following conclusion of both Study Phases to account for any relevant data that may have not been collected during the Study.

---

-----Start of In-person Phase-----

---

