### 3.2 END OF STUDY DEFINITION

A Participant is considered to have completed the Study if he/she/they have remained a Participant for the entirety of the Study period and have completed the applicable end of Study REDCap Cloud survey. Therefore, up to 14 days for the At-home Phase, including Study intervention, is sufficient time to collect data and evaluate the interventional device. Since Study Sites are required to see all Participants after the At-home Phase, up to 28 days for the In-person Phase is sufficient time to see all Participants as patients through already scheduled visits, overbookings or separate dedicated clinics. Biopsy results typically take 7 days to follow up, however Study Coordinators will continue to monitor EMR of Participants to collect relevant data up to 30 days following the end of the Study.

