## 8.8     **FOLLOW-UP**

There will be no scheduled follow-up after completion of the Study. Any follow up for Participants after conclusion of the 42 day Study will be part of the Participant's standard clinical care pathways and not the responsibility of Study Coordinators or the Study Sponsor.

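### Adverse-event recording stops at the last day of participation, when the exam and biopsy may only just have happened, so whether a biopsy complication is counted depends on visit timing

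*Combined protocol and SAP*

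**What the plan says.** Section 10.5 fixes the window by start date: "The Investigator will record all reportable events with start dates occurring any time after enrollment until the last day of Study participation". The AE definition in section 10.2.1 closes at the same point, covering signs or symptoms "from the time of signing the informed consent to completion of the Study". Dataset L in section 3.1 counts AEs reported during the Study, and section 11.4.4 tabulates on-study AEs, so the safety table inherits this limit.

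The Synopsis gives the At-home Phase as "Up to 14 days, completed by Participants at their home address" and the In-person Phase as up to 28 days. Section 8.9 asks for the exam within 28 days of finishing the At-home Phase. The schedule of events (section 8.10) puts the closing survey at Day 42, with a tolerance of 3 days.

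Three statements cover what happens next:
- Section 3.1: "Participant EMRs will be monitored for up to 28 days following conclusion of both Study Phases".
- Section 3.2: "Biopsy results typically take 7 days to follow up", and "Study Coordinators will continue to monitor EMR of Participants to collect relevant data up to 30 days following the end of the Study".
- Section 8.8: "There will be no scheduled follow-up after completion of the Study". It adds that care after the 42-day Study is not the coordinators' responsibility.

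Section 1.3.1 lists a possible rise in biopsies, with their attendant risks, among the known potential risks. Section 10.5 asks that on-study AEs be documented whether or not they are related to the product.

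**The concern.** Any biopsy follows the exam at the in-person visit. If that visit is early in its window, several weeks remain in which a complication can start and be recorded. If it is on the last permitted day, none remain. The two participants carry the same risk, but only one can contribute a post-biopsy event to the safety table. Following AEs to resolution does not help, because the rule acts on when the event starts. The post-study chart review does not help as written either: it is there to gather relevant data, and nothing in the plan extends AE recording into it.

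At stake is even ascertainment of a risk that the protocol itself names. A count of biopsy complications would be too low by an amount set by scheduling.

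**Working it through.** **Length of participation.** At-home maximum 14 days + In-person maximum 28 days = 42 days. This reproduces the 42-day Study of section 8.8 and the Day 42 survey of section 8.10. Day 42 is still an inference, because section 10.5 gives no day number.

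**Latest biopsy.** Day 14 + 28 = day 42. AE capture left after it: 42 − 42 = 0 days.

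**Share of visits with little capture left.** The plan gives neither a distribution of visit days nor a time to onset for biopsy complications. As a yardstick I use 7 days, the only post-biopsy interval in the plan (the usual wait for a result, section 3.2), and ask how many visits fall after day 42 − 7 = 35. Each row is an assumption.

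| Assumption | Visits after day 35 | Mean capture to day 42 |
|---|---|---|
| At-home time uniform on 0–14 days, visit uniform on 0–28 days later | (7 × 7 ÷ 2) ÷ (14 × 28) = 24.5 ÷ 392 = 6.25% | 42 − (7 + 14) = 21 days |
| All 14 at-home days used, visit uniform over days 14–42 | 7 ÷ 28 = 25% | 14 days |
| All visits in the last two weeks, uniform over days 28–42 | 7 ÷ 14 = 50% | 7 days |

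The third row only shows what late clustering would do; nothing in the text says that visits will cluster.

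**Survey tolerance.** If the last day moves between 39 and 45 and visits are as in the second row, the share with less than 7 days left runs from 10 ÷ 28 = 36% (last day 39) to 4 ÷ 28 = 14% (last day 45).

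**Effect of using the chart review already planned.** The window would end at day 42 + 28 = 70 (section 3.1) or day 42 + 30 = 72 (section 3.2). A day-42 biopsy would then have 28 to 30 days of AE capture in place of 0.

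**The case against.** The strongest reply is that this says little about the device. Section 10.2.1 ties an AE to use of the Sklip System. Biopsy is standard care, chosen by a provider who is blinded to the at-home findings (sections 5.3.1 and 8.1.2), and section 1.3.1 itself attributes the decision to the provider and not to the device. Most complications missed would be unrelated to the product. That stands, and it limits how much the point matters. It does not remove it: section 10.5 requires recording regardless of relationship, so complications of early biopsies will be in the table, and section 1.3.1 presents biopsy risk as a risk of this study.

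Several provisions soften the gap. Section 10.5 has the investigator ask about AEs at elective follow-up visits, but those are optional and the start-date limit still applies. Unanticipated problems and unanticipated device effects have their own reporting route (sections 10.2.3, 10.6.1 and 10.6.3) with no start-date limit stated there, so a serious unexpected device event is not lost. Ending AE onset at the end of participation is also a common choice, and safety here is descriptive only.

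A reader might infer that the window also cuts off psychological stress, the one event of special interest in section 10.4.3. The documents do not support that. The stress example in section 10.2.1 concerns self-skin-exams, which belong to the first 14 days and so leave about 42 − 14 = 28 days of capture. No section names distress at a biopsy result as a harm.

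**Conclusion.** The point holds in a limited form. As written, the AE onset window can close on the day of a late biopsy, so ascertainment of a protocol-named risk is uneven across participants. This rests on reading the last day of participation as about day 42.

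The size is unknown. About 6% to 25% of visits would leave less than 7 days of capture under two equally arbitrary assumptions, and more if visits cluster late. A reader might take 25% or 50% as the share of complications lost. It is not: these are shares of visits, the 25% assumes that everyone uses all 14 at-home days when the plan says up to 14, and the plan gives no complication rate from which to count lost events.

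The primary and exploratory endpoints are unaffected. This is an inexpensive improvement to safety recording, not a flaw in the accuracy analysis.

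**What to change.** - **Sections 10.5 and 10.2.1:** define the last day of Study participation, and extend the AE onset window, at least for biopsy-related events, to the end of the chart review already planned.
- **Sections 3.1, 3.2 and 8.8:** reconcile the 28-day and 30-day chart-review figures, and reconcile both with the statement that follow-up after the 42-day Study is not the coordinators' responsibility.
- **Section 11.4.4:** tabulate AEs before and after the in-person visit, and flag those found by chart review, since they were not elicited by asking the participant.

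No clinical care changes, and the same coordinators already read the same charts. The cost is more than wording, though. Each added AE needs severity grading (section 10.2.4), a causality judgement by the examining clinician (section 10.2.5) and reporting within 7 days of notification to the site's own IRB and to the lead site (section 10.6.2). A few more AEs, mostly unrelated to the device, would be listed. Passive chart review will also miss most self-reported distress, so the change should not be presented as improving capture of that event.
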